Risks associated with the use of adalimumab are well characterized, and are described in approved local product information. Adalimumab is associated with an increased risk for developing serious infections that may lead to hospitalization or death. Opportunistic infections due to bacterial, mycobacterial, invasive fungal, viral, parasitic, or other opportunistic pathogens have been reported with TNF α inhibitors. Reactivation of latent TB has been reported. All subjects will be tested for TB before study start as outlined in the exclusion criteria and will be carefully monitored for signs and symptoms of infection during and after the study. Study drug will be discontinued for serious infections as outlined in section 3.5. An increase of non-melanoma skin cancers, hematologic cancers and a potential increase of other cancers has been reported with use of TNF α inhibitors. Subjects will undergo regular assessments, including physical examination and haematological assessments.

TNF α inhibitors are commonly used as first line therapy in MTX-IR RA patients. Their efficacy in this patient population has been well established. Overall, the benefit of using adalimumab as proposed in this study is considered to outweigh any associated risks.

An independent data monitoring committee (DMC) appointed to monitor the study (with an interim safety analysis after the first 100 subjects complete 12 weeks of treatment) will provide an additional level of risk mitigation.

The overall risk:benefit balance of this study is considered favorable. For additional information about the risks of filgotinib, reference is made to the investigator brochure.

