8.9. Sample Size

Sample size is determined based on the superiority test of filgotinib 200 mg compared to placebo based on the change from Baseline in mTSS at Week 24. When assuming a difference of 0.4 between filgotinib and placebo on change from Baseline in mTSS at Week 24 and a common standard deviation of 1.85, 450 subjects in each of the filgotinib 200 mg group and placebo control group are required to obtain 90% power at a 2-sided 0.05-level.

A sample size of 450 subjects in each of the filgotinib groups and placebo control group will provide over 95% power to detect an increase in ACR20 response rate of 45% to 65% between the placebo control group and the filgotinib group respectively, using a 2-sided 0.05-level test.

Based on {Liu et al 2014}, 450 subjects in each of the filgotinib 200 mg group and placebo group, and 300 subjects in the adalimumab group, will provide over 90% power at 2-sided 0.05 significance level to demonstrate that filgotinib 200 mg preserves more than 50% of the effect of adalimumab with respect to the response rate of DAS28 (CRP) \leq 3.2 at Week 12, assuming both filgotinib 200 mg and adalimumab groups have similar response rates of DAS28 (CRP) \leq 3.2. Given this study has a placebo group, assay sensitivity can be established through a direct comparison of adalimumab to placebo.

In summary, the total sample size will be 1650 (450 for the filgotinib 200 mg, filgotinib 100 mg, placebo groups, and 300 for the active comparator group).

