3.5. Multiple Comparisons

The primary endpoint for the study is the proportion of subjects who achieve an ACR20 response at Week 12. The primary analyses will consist of a superiority test of filgotinib 200 mg compared to placebo based on the ACR20 response rate at Week 12.

The following hypothesis testing for secondary analyses will commence after the primary analysis reaches statistical significance, and will be tested according to the hierarchical testing principle at the 2-sided 0.05 level. If a null hypothesis is not rejected, formal sequential testing will be stopped and only nominal significance will be reported for the remaining hypotheses:

- 1) Superiority of filgotinib 100 mg compared to placebo based on ACR20 response rate at Week 12
- 2) Superiority of filgotinib 200 mg compared to placebo based on the change from Baseline in HAQ-DI at Week 12
- 3) Superiority of filgotinib 100 mg compared to placebo based on the change from Baseline in HAQ-DI at Week 12
- 4) Superiority of filgotinib 200 mg compared to placebo based on the proportion of subjects with DAS28(CRP) < 2.6 at Week 12
- 5) Superiority of filgotinib 100 mg compared to placebo based on the proportion of subjects with DAS28(CRP) < 2.6 at Week 12
- 6) Superiority of filgotinib 200 mg compared to placebo based on the change from Baseline in mTSS at Week 24
- 7) Superiority of filgotinib 100 mg compared to placebo based on the change from Baseline in mTSS at Week 24
- 8) Non-inferiority of filgotinib 200 mg compared to adalimumab based on the proportion of subjects with DAS28(CRP) ≤ 3.2 at Week 12

- 9) Non-inferiority of filgotinib 100 mg compared to adalimumab based on the proportion of subjects with $\text{DAS28(CRP)} \leq 3.2$ at Week 12
- 10) Superiority of filgotinib 200 mg compared to placebo based on the change from Baseline in SF-36 PCS at Week 12
- 11) Superiority of filgotinib 100 mg compared to placebo based on the change from Baseline in SF-36 PCS at Week 12
- 12) Superiority of filgotinib 200 mg compared to placebo based on the change from Baseline in FACIT-Fatigue at Week 12
- 13) Superiority of filgotinib 100 mg compared to placebo based on the change from Baseline in FACIT-Fatigue at Week 12
- 14) Superiority of filgotinib 200 mg compared to adalimumab based on the proportion of subjects with $\text{DAS28(CRP)} \leq 3.2$ at Week 12

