- 15) Superiority of filgotinib 100 mg compared to adalimumab based on the proportion of subjects with $\text{DAS28(CRP)} \leq 3.2$ at Week 12
- 16) Non-inferiority of filgotinib 200 mg compared to adalimumab based on the proportion of subjects with $\text{DAS28(CRP)} < 2.6$ at Week 12
- 17) Non-inferiority of filgotinib 100 mg compared to adalimumab based on the proportion of subjects with $\text{DAS28(CRP)} < 2.6$ at Week 12
- 18) Superiority of filgotinib 200 mg compared to adalimumab based on the proportion of subjects with $\text{DAS28(CRP)} < 2.6$ at Week 12
- 19) Superiority of filgotinib 100 mg compared to adalimumab based on the proportion of subjects with $\text{DAS28(CRP)} < 2.6$ at Week 12

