 - If a subject takes standard of care medications due to inadequate response or discontinues from study treatment, treat data as missing from the point of inadequate response or study drug discontinuation (ie, on-treatment data defined above).
 - If a subject discontinues from the study, treat data as missing from the point of loss to follow-up onward.
- 4) Population-level summary: proportion difference for binary efficacy endpoints or mean difference in change from baseline for continuous efficacy endpoints between each filgotinib group and placebo group or adalimumab group if applicable.

The **Treatment-Policy Estimand** is defined as following. This is the secondary estimand for efficacy endpoints.

- 1) Population: Subjects in the FAS.
- 2) Variable: Primary and key secondary endpoints as well as some other secondary endpoints (see details in Section 6.2, 6.3 and 6.4)
- 3) Intercurrent events: The occurrence of an intercurrent event is irrelevant. All observed values will be used regardless of occurrence of an intercurrent event.
 - All observed values will be used regardless of occurrence of an intercurrent event (ie, All available data defined above).
 - If a subject discontinues from the study, treat data as missing from the point of loss to follow-up onward.
- 4) Population-level summary: Proportion difference for binary efficacy endpoint or mean difference in change from baseline for continuous efficacy endpoints between each filgotinib group and placebo group or adalimumab group if applicable.

The other secondary endpoints specified in both estimands include ACR50, ACR70, and the individual components of the ACR response.

To handle the missing data caused by the intercurrent events, the following analyses will be performed for both estimands:

- For binary endpoints, missing data will be treated as non-responder for the primary analysis. Sensitivity analyses including observed data only, last observation carry forward (LOCF), multiple imputation, and tipping point methods will be applied.
- For continuous endpoints, missing data will be handled using a mixed-effects model for the primary analysis. Sensitivity analyses, including using multiple imputation and tipping point methods, will be applied.

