6.2.3. Primary Analysis of the Primary Efficacy Endpoint

To test for superiority of filgotinib 200 mg group versus placebo control group in proportion of subjects who achieve ACR20 at Week 12, a logistic regression analysis with treatment groups and stratification factors in the model will be used. The model will include all treatment groups. Subjects who do not have sufficient measurements to establish efficacy at Week 12 will be considered as failures (ie, NRI). The p-value from the logistic regression model for testing the superiority of filgotinib 200 mg as compared to placebo will be provided. The 2-sided 95% confidence interval (CI) of the ACR20 response rate at Week 12 based on normal approximation with the sample variance will be provided for each treatment group. In addition, non-stratified ACR20 response rate difference along with its 95% CI calculated based on the normal approximation with the pooled sample variance will be provided. [Appendix 8](#) provides samples SAS model statements for constructing the confidence interval for the proportion.

The comparisons of filgotinib 100 mg groups versus placebo group in the proportion of subjects achieving ACR20 at Week 12 will also be conducted with the similar logistic regression model with NRI as aforementioned.

The number and percentage of ACR20 non-responders observed and non-responders due to missing at Week 12 will also be summarized respectively by treatment.

For subjects with observed ACR20 outcomes (ie, responders and observed non-responders) at Week 12, actual values and change from Baseline at Week 12 in individual components, including TJC68, SJC66, SGA, PGA, Subject's pain assessment, hsCRP, will be summarized using descriptive statistics (sample size, mean, SD, median, Q1, Q3, minimum, and maximum) by treatment.

The proportions of subjects achieving ACR20 (using NRI) will be plotted over time from Baseline through Week 24 by treatment and by visit.

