6.3.2. Analysis Methods for Key Secondary Efficacy Endpoints

Hypothesis testing on the key secondary efficacy endpoints will commence after the testing on the primary efficacy endpoint reaches statistical significance, and will be performed according to the hierarchical testing principle at the 2-sided 0.05 level as described in Section 3.5. If a null hypothesis is not rejected, formal sequential testing will be stopped and only nominal significance will be reported for the remaining hypotheses.

For non-inferiority test of the proportion of subjects who achieve $\text{DAS28}(\text{CRP}) \leq 3.2$ at Week 12, the approach proposed by {Liu 2014} will be used to demonstrate that each filgotinib dose preserves more than 50% of the effect of adalimumab on the response rate of DAS28 (CRP) ≤ 3.2 at Week 12 using NRI. Let π_T , π_C and π_P denote the true response rates of DAS28 (CRP) ≤ 3.2 for filgotinib, adalimumab, and placebo respectively, at Week 12, with corresponding variances σ_T^2 , σ_C^2 and σ_P^2 . The non-inferiority null hypothesis is

$$H_{0,NI} : \frac{\pi_T - \pi_P}{\pi_C - \pi_P} \leq 0.5$$

According to {Liu 2014}, non-inferiority (filgotinib preserves more than 50% of the effect of adalimumab) at 2-sided 0.05 level will be claimed if $Z_{NI} > z_*$, where

$$Z_{NI} = \frac{\hat{\pi}_T - 0.5\hat{\pi}_C - (1-0.5)\hat{\pi}_P}{\sqrt{\hat{\sigma}_T^2 + 0.5^2\hat{\sigma}_C^2 + (1-0.5)^2\hat{\sigma}_P^2}}$$
 and z_* is the 97.5 quantile of the standard normal distribution.

Note that the “hat” (^) denotes the estimated values of each parameter at Week 12.

The non-inferiority test of the proportion of subjects who achieve $\text{DAS28}(\text{CRP}) < 2.6$ at Week 12 will be performed.

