For the superiority test of the proportion of subjects who achieve DAS28(CRP) < 2.6 at Week 12, the similar logistic regression analysis with the same model specification as the primary endpoint analysis described in Section 6.2.3 will be adopted for the treatment comparisons. The model will include all treatment groups. The NRI method will be used to impute missing value. Comparison will be made between each filgotinib dose group and placebo group. The p-value from the logistic regression model will be reported for statistical inference. The 2-sided 95% CI of response rate based on normal approximation with the sample variance will be provided for each treatment group. In addition, non-stratified response rate difference along with its 95% CI calculated based on the normal approximation with the pooled the sample variance will be provided. The superiority test of the proportion of subjects who achieve DAS28(CRP) \leq 3.2 or DAS28(CRP) < 2.6 at Week 12 will be performed in the similar way, and the comparison will be made between each filgotinib dose group and adalimumab group.

The change from Baseline in HAQ-DI at Week 12 will be analyzed using the mixed-effects model for repeated measures (MMRM) that includes data at postbaseline visits up to the time point of interest. Subjects that have a baseline value and at least 1 postbaseline value are included in the analysis. The MMRM models will be used to evaluate treatment effect on change score from Baseline, with baseline value, stratification factors, treatment, visit, and treatment by visit interaction included as fixed effects and subject being the random effect. The MMRM model will include all treatment groups. An unstructured variance-covariance matrix will be used. The Kenward-Roger method will be used to estimate the degrees of freedom. Missing change scores due to missing study visits, early withdrawal or treatment reassignment will not be otherwise imputed using the MMRM approach. The least squares (LS) means and 95% CIs of the difference in mean change from Baseline in HAQ-DI between each filgotinib dose group and placebo group from MMRM will be provided.

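### The adalimumab effect-preservation claim carries no written condition that adalimumab beats placebo, and the adalimumab-placebo comparison named for assay sensitivity is not a planned analysis

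*SAP*

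**What the plan says.** SAP 6.3.2, repeating protocol 8.5.2, writes the non-inferiority null as (π_T − π_P)/(π_C − π_P) ≤ 0.5, where T is filgotinib, C adalimumab and P placebo. The decision rule follows: "non-inferiority (filgotinib preserves more than 50% of the effect of adalimumab) at 2-sided 0.05 level will be claimed if" Z_NI > z*, with z* = 1.96. Z_NI uses the linear contrast π_T − 0.5π_C − 0.5π_P. Neither document writes π_C > π_P beside the rule.

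In the SAP 3.5 hierarchy the first use is "8) Non-inferiority of filgotinib 200 mg compared to adalimumab based on the proportion of subjects with" DAS28(CRP) ≤ 3.2 at Week 12, with step 9 for 100 mg. The second is "16) Non-inferiority of filgotinib 200 mg compared to adalimumab based on the proportion of subjects with" DAS28(CRP) < 2.6, with step 17 for 100 mg. SAP 6.3.3.3 reuses the rule with retention fractions up to 0.99.

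Protocol 8.9 and SAP 1.3 say that "assay sensitivity can be established through a direct comparison of adalimumab to placebo".

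The planned contrasts are these:
- The estimands in SAP 6.1 are defined "between each filgotinib group and placebo group or adalimumab group if applicable".
- The superiority tests against adalimumab in SAP 6.3.2 specify that "the comparison will be made between each filgotinib dose group and adalimumab group".
- The remaining tests in SAP 3.5, 6.3.2, 6.3.3 and 6.4.2 compare filgotinib with placebo, with adalimumab or with the placebo-switch groups, or reuse Z_NI.

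None sets adalimumab against placebo.

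**The concern.** Moving from the ratio null to the linear statistic means multiplying through by π_C − π_P, which keeps the inequality only when that difference is positive. If it is zero, the ratio is undefined. If adalimumab is below placebo and filgotinib above it, the ratio is negative, so the null as written is true, yet a large Z_NI rejects it.

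The tests before step 8 do not cover this. The primary test and steps 1-7 all compare filgotinib with placebo, so they show that filgotinib works and say nothing about adalimumab. At stake is a formal statement, for two doses and two endpoints, that more than half of adalimumab's effect has been retained, in a trial that may not have shown any adalimumab effect. Filgotinib's own activity is not in question.

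**Working it through.** **Inputs.** n = 450 filgotinib, 300 adalimumab, 450 placebo (SAP 1.3); z* = 1.96 and retention 0.5 (SAP 6.3.2). The documents give no DAS28(CRP) response rates, so every rate below is an assumption, written filgotinib/adalimumab/placebo in percent.

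**Formulas.** With v = p(1 − p)/n:
- Z_NI has mean (p_T − 0.5p_C − 0.5p_P)/√(v_T + 0.25v_C + 0.25v_P).
- The adalimumab-placebo z has mean (p_C − p_P)/√(v_C + v_P).
- The two numerators have covariance −0.5v_C + 0.5v_P.
- Joint probabilities come from the bivariate normal.

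**The plan's own figures first.** The mTSS sizing (0.4, SD 1.85, 450 per arm) gives 90.0% power, as stated. The non-inferiority power of over 90% cannot be reproduced without rates. With filgotinib equal to adalimumab, 90% power needs a common effect over placebo of 17.7, 18.5, 19.0, 19.2 or 19.3 points at placebo 15, 20, 25, 30 or 35%. At 45/45/25 the numerator is 0.10 and the SE 0.0293, so the mean is 3.409 and power is Φ(3.409 − 1.96) = 92.6%.

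**Two cases where the rule misfires.**
- 35/25/25: numerator 0.35 − 0.125 − 0.125 = 0.10; SE = √(0.000506 + 0.000156 + 0.000104) = 0.0277; mean 3.613; P(Z_NI > 1.96) = Φ(1.653) = 95.1%.
- 35/20/25: numerator 0.35 − 0.10 − 0.125 = 0.125; SE 0.0273; mean 4.586; P = Φ(2.626) = 99.6%. The true ratio is 0.10/(−0.05) = −2, inside the stated null.

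As a single data set, observed rates of 40/22/25 give Z_NI = 5.91 and a ratio of −5.0, with adalimumab-placebo z = −0.95.

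**With and without a condition that adalimumab is superior to placebo (2-sided 0.05):**

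| Rates | True ratio | Z_NI passes | Both pass |
|---|---|---|---|
| 35/20/25 | −2 | 99.6% | 0.02% |
| 30/20/25 | −1 | 80.7% | 0.01% |
| 30/20/20 | undefined | 96.8% | 2.4% |
| 35/25/25 | undefined | 95.1% | 2.3% |
| 40/30/30 | undefined | 93.6% | 2.2% |
| 45/45/25 | 1 | 92.6% | 92.6% |
| 40/40/25 | 1 | 73.6% | 72.8% |
| 35/35/25 | 1 | 42.4% | 33.5% |

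**Type I error when adalimumab works.** At a ratio of exactly 0.5 (30/35/25, 27.5/30/25, 32.5/40/25) the numerator is 0, so rejection is 2.5% each time.

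**Check with the logistic model.** A simulation of 6,000 trials per scenario used an all-arm main-effects model for the adalimumab-placebo condition. The strata mix was assumed: regions 30/40/12/10/8%, prior bDMARD 10%, seropositive 80%. It gave 99.6% and 0.02% at 35/20/25, 94.6% and 2.4% at 35/25/25, and 92.6% and 92.6% at 45/45/25.

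The figures treat Z_NI by itself, so they are upper bounds for the claim as planned. The two mTSS steps, for example, pass together about 83% of the time (assuming the same effect for 100 mg and correlation 0.5).

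**The case against.** **The step may be in the source.** The SAP adopts a published three-arm method by citation, and that paper's title refers to a step-down hierarchical model. The assay-sensitivity sentence directly follows a citation of it. This stands in part. The paper cannot be checked here, so a reader should not infer that the method lacks the step, only that the SAP does not write it out.

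**Adalimumab's efficacy is not in doubt.** Protocol 1.5 says of TNFα inhibitors: "Their efficacy in this patient population has been well established". This bears on how likely the problem is, and it is why the practical risk is small. Assay sensitivity, however, is a property of this trial, and the plan itself says it is to be shown by direct comparison.

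**The filgotinib conclusion would still be right.** At 35/20/25 and 35/25/25 filgotinib is truly better than adalimumab, and step 14 taken by itself would have 99.6% and 84.5% power. This stands: the faulty part is the wording about retained effect, not a finding that filgotinib is no worse.

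**The arms can already be compared.** Response rates with 95% CIs are planned for every arm. That helps a reader, but no adalimumab-placebo difference is specified and nothing ties it to the claim.

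**A hard gate would do harm.** If failure of the condition stopped testing at step 8, the extra chance of stopping would be up to 17% at 45/35/25 and 68% at 45/30/25. The retention claim is true in both cases (ratios 2 and 4). SF-36 PCS and FACIT-Fatigue against placebo (steps 10-13) and superiority over adalimumab (steps 14-15) would then lose formal testing. This objection stands and determines the form of the fix.

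**Conclusion.** The gap is real but narrow. The written rule can reject its own null when that null is true, but only if adalimumab is worse than placebo. If adalimumab equals placebo, the claim refers to an effect that does not exist. Under the assumed rates, Z_NI passes 80.7-99.6% of the time in those cases.

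Three stronger readings are tempting, and the documents do not support them:
- **That the non-inferiority test is generally anti-conservative.** It is not: the error is at most 2.5% for any positive adalimumab effect.
- **That the claim rests on Z_NI with nothing before it.** The primary test and steps 1-7 must pass first, although none concerns adalimumab.
- **That claims made without a significant adalimumab effect are errors.** At 45/30/25 (68%) and 45/35/25 (17%) the claims are true. They only lack demonstrated assay sensitivity.

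At the effect that 90% non-inferiority power needs, the share of claims made without a significant adalimumab effect is 0.02-0.04%. The gap matters when adalimumab underperforms, which is when assay sensitivity is needed.

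**What to change.** In SAP 6.3.2, before unblinding:
1. State π_C > π_P as part of the non-inferiority hypothesis.
2. Pre-specify adalimumab versus placebo on the same endpoint (FAS, NRI, 2-sided 0.05), using the logistic model of SAP 6.2.3, which already covers adalimumab: "The model will include all treatment groups".
3. Report that difference with its 95% CI beside each non-inferiority result: steps 8-9 (≤ 3.2), steps 16-17 (< 2.6) and the margins in 6.3.3.3.
4. Use the statement that more than half of adalimumab's effect is retained only if adalimumab is superior to placebo on that endpoint.

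Apply item 4 to the claim, not as a gate. The rejection rule for Z_NI and the order of SAP 3.5 stay as they are, so steps 10-15 are not stopped by it. Z_NI tests the linear inequality at 2.5% whatever the sign of π_C − π_P, so continuing down the hierarchy stays valid. No alpha is added, because the claim now needs two results instead of one. If the cited method already contains the step, items 1 and 2 simply write it in.

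The cost is a few sentences and no new data. The preservation claim is lost when adalimumab does not separate from placebo: power for that claim is unchanged at 92.6% (45/45/25), and falls from 73.6% to 72.8% (40/40/25) and from 42.4% to 33.5% (35/35/25).

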1.3. Sample Size and Power

Sample size is determined based on the superiority test of filgotinib 200 mg compared to placebo based on the change from Baseline in mTSS at Week 24. When assuming a difference of 0.4 between filgotinib and placebo on change from Baseline in mTSS at Week 24 and a common standard deviation of 1.85, 450 subjects in each of the filgotinib 200 mg group and placebo control group are required to obtain 90% power at a 2-sided 0.05-level.

A sample size of 450 subjects in each of the filgotinib groups and placebo control group will provide over 95% power to detect an increase in ACR20 response rate of 45% to 65% between the placebo control group and the filgotinib group respectively, using a 2-sided 0.05-level test.

Based on {Liu 2014}, 450 subjects in each of the filgotinib 200 mg group and placebo group, and 300 subjects in the adalimumab group, will provide over 90% power at 2-sided 0.05 significance level to demonstrate that filgotinib 200 mg preserves more than 50% of the effect of adalimumab with respect to the response rate of DAS28(CRP) ≤ 3.2 at Week 12, assuming both filgotinib 200 mg and adalimumab groups have similar response rates of DAS28(CRP) ≤ 3.2 . Given this study has a placebo group, assay sensitivity can be established through a direct comparison of adalimumab to placebo.

In summary, the total planned sample size will be 1650 (450 for the filgotinib 200 mg, filgotinib 100 mg, placebo groups, and 300 for the active comparator group).

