The change from Baseline in mTSS, erosion score and JSN score at Week 24, and change from Baseline in SF-36 PCS score and FACIT-Fatigue score at Week 12 will be analyzed using similar MMRM method as HAQ-DI, by including data at postbaseline visits up to the time point of interest. To test for a treatment difference between each filgotinib dose group and placebo, LS mean difference along with 95% CI and p-values from the MMRM model will be presented.

The proportions of subjects achieving DAS28(CRP) \leq 3.2 (using NRI), and proportions of subjects achieving DAS28(CRP) < 2.6 (using NRI) will be plotted over time by treatment. Plots of mean \pm SD of changes from Baseline in HAQ-DI, mTSS, erosion score, JSN score, SF-36 PCS and FACIT-Fatigue over time will be presented respectively. Cumulative percentile plots will be provided for change from baseline in mTSS.

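### The Week 24 mTSS model shares one covariance matrix over all four arms; if the placebo SD is 1.3 to 1.6 times that of 200 mg and adalimumab (an assumption), the 100 mg test runs at about 8-10% two-sided instead of 5%

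*SAP*

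**What the plan says.** SAP 6.3.2 sets out the repeated-measures model for HAQ-DI: "The MMRM model will include all treatment groups. An unstructured variance-covariance matrix will be used", with Kenward-Roger degrees of freedom. The next paragraph extends it. Changes in mTSS, erosion score and JSN score at Week 24 "will be analyzed using similar MMRM method as HAQ-DI, by including data at postbaseline visits up to the time point of interest". SAP 6.4.2 describes the same all-arms, unstructured model again and names mTSS among its endpoints. Neither section mentions a matrix by arm or a robust variance, so one matrix shared by the four arms is the plain reading.

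In the testing order of SAP 3.5, test 6 is 200 mg versus placebo on mTSS. Test 7 is: "Superiority of filgotinib 100 mg compared to placebo based on the change from Baseline in mTSS at Week 24". Tests 8 to 19 follow it in the fixed sequence.

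The only spread the documents give for mTSS change is the planning value in SAP 1.3 (also Protocol 8.9): "a common standard deviation of 1.85".

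**The concern.** A shared matrix is a mild assumption for HAQ-DI. For radiographic change it deserves a second look. If many subjects hardly progress, the mean is carried by a minority who do, and a drug that reduces their number lowers the mean and the SD together. The shared variance is then an average weighted towards the less variable arms, and it is too small for a contrast that involves placebo. Kenward-Roger does not correct this, because it adjusts for estimating the assumed matrix and not for the matrix being wrong.

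Test 7 is the sensitive place. It supports the joint-structure claim for the lower dose, and a false rejection lets the sequence run on to twelve further tests. If 100 mg truly does nothing, it has placebo's wide spread, yet its standard error is reduced by the 200 mg and adalimumab arms. The confidence interval for 200 mg minus placebo would also be too narrow.

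**Working it through.** **Inputs from the documents.** Arm sizes: "450 for the filgotinib 200 mg, filgotinib 100 mg, placebo groups, and 300 for the active comparator group" (1650 in all). Test level: two-sided 0.05. Planning SD: 1.85. Postbaseline radiographs up to Week 24: Weeks 12 and 24 (Protocol Appendix 2).

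**Input not in the documents.** The SD ratio r = placebo SD / effective-arm SD. It is an assumption throughout.

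**The plan's own figure.** "When assuming a difference of 0.4 between filgotinib and placebo on change from Baseline in mTSS at Week 24", with SD 1.85 and 90% power:

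n per arm = 2 × (1.960 + 1.282)² × 1.85² / 0.4² = 449.5, so 450. This reproduces the plan.

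**Test 7 when 100 mg equals placebo, and 200 mg and adalimumab have the smaller SD.** With placebo variance set to 1, 900 subjects have variance 1 and 750 have 1/r². So

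v = shared variance / true variance = (900 + 750/r²) / 1650, and actual two-sided error = 2 × [1 − Φ(1.96 × √v)].

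| r | v | Two-sided error | Favourable direction (half) |
|---|---|---|---|
| 1.0 | 1.000 | 5.0% | 2.5% |
| 1.2 | 0.861 | 6.9% | 3.4% |
| 1.3 | 0.814 | 7.7% | 3.8% |
| 1.5 | 0.747 | 9.0% | 4.5% |
| 1.6 | 0.723 | 9.6% | 4.8% |
| 2.0 | 0.659 | 11.2% | 5.6% |

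**If only 200 mg has the smaller SD:** v = (1200 + 450/r²) / 1650. The error is 6.3% at r = 1.25 and 8.0% at r = 2.0.

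**If 100 mg also has the smaller SD but placebo's mean:** 6.3% at r = 1.25 and 9.4% at r = 2.0.

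**Coverage of the 200 mg minus placebo 95% interval, all active arms having the smaller SD.** With their variance set to 1, the model variance is proportional to 2 × (1200 + 450r²) / 1650 and the true variance to 1 + r². At r = 1.2 this is 2.24 against 2.44, coverage 94.0%. At r = 1.5 it is 2.68 against 3.25, coverage 92.5%. At r = 2.0 it is 3.64 against 5.00, coverage 90.5%.

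**Where the band 1.3-1.6 comes from.** It comes from a simple mixture: 15-30% of placebo subjects progress by an exponential amount, reading error has SD 0.5, the placebo mean is 0.5-1.0, and the drug lowers the mean by 0.4 by reducing the number of progressors. As an example, take 20% progressing and mean 0.7, so mean size 0.7/0.20 = 3.5.

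- Placebo variance = 2 × 0.20 × 3.5² − 0.7² + 0.25 = 4.66, SD 2.16.
- Drug: 0.20 × 0.3/0.7 = 8.57% progress; variance = 2 × 0.0857 × 3.5² − 0.3² + 0.25 = 2.26, SD 1.50.
- Ratio 1.44; root mean square SD √[(4.66 + 2.26)/2] = 1.86, close to the plan's 1.85.

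Mixtures of this kind near 1.85 have ratios of about 1.3-1.6. If the drug instead shrinks each progression, the same grid gives about 1.6-3.0. The ratio depends on the assumed mechanism and is not an estimate for this trial.

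**Simulation.** A two-visit model was run 10,000 times per setting with normal and skewed data, complete or with 10-25% missing at Week 24 (assumed), and a Week 12-Week 24 correlation of 0.7 (assumed). In the first scenario the shared matrix gave 4.8-5.1% at r = 1, 7.1-7.7% at r = 1.25 and 11.4-11.9% at r = 2. Estimating the covariance by arm gave 4.8-5.3% throughout. At r = 1.25 and 2.0, test 6 passed in 92-99% of runs, so it offers test 7 almost no protection.

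**The case against.** The strongest reply is that the decisive input is missing. The only stated SD is common to all arms, and at that value the test runs at exactly its level. This stands: a reader might infer that the type I error of test 7 is not held at 5%, but the documents support that only if the spreads differ.

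Other tempting readings also go too far:

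- **An 11% headline.** It needs a ratio of 2.0, above the 1.3-1.6 band. The figures are also two-sided; a false claim of benefit occurs at about half of them.
- **Skewness as a finding of the SAP.** The SAP 6.4.2 cut-offs for no progression (0, 0.5 and the smallest detectable change) define a responder endpoint. They do not describe the distribution of mTSS change or its variance by arm.
- **Smaller variances established by the testing order.** Passing test 6 shows a difference in means. Nothing in the sequence tests adalimumab on mTSS, so its smaller spread is assumed.
- **Loss of placebo films making matters worse.** Excluding data after inadequate response at Week 14 could lower placebo's weight. It could equally trim its upper tail and narrow the gap. The effect of that rule was not modelled.

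The plan would also make unequal spread visible. SAP 6.3.2 provides plots of mean with SD and cumulative percentile plots, SAP 6.4.2 gives descriptive statistics by arm, and the logistic analysis of non-progression needs no common mTSS variance. These limit the risk of an unnoticed error but do not correct the p-value of test 7.

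The planned sensitivity analyses do not fill the gap. Multiple imputation and tipping point reuse the 6.3.2 model, and the per-protocol repeat leaves out mTSS (SAP 6.3.3). Elsewhere the plan does not insist on equal variances: its non-inferiority statistic uses a separate variance for each arm.

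**Conclusion.** The concern holds conditionally. As written, the mTSS tests depend on equal spread in all four arms, and no planned analysis relaxes that. With equal SDs there is no error. For an assumed placebo/effective-arm SD ratio of 1.3-1.6, with 100 mg behaving like placebo and both 200 mg and adalimumab less variable, test 7 runs at about 8-10% two-sided (about 4-5% in the favourable direction, against 2.5%). Over ratios 1.0-2.0 the range is 5-11%, and it is lower if only 200 mg is less variable. The 200 mg interval covers about 94.0% to 90.5% at ratios 1.2-2.0 if all active arms are less variable. This is a cheap and worthwhile improvement to the model, not evidence that the trial's error rate is wrong.

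**What to change.** In SAP 6.3.2 for mTSS, erosion and JSN scores, and in SAP 6.4.2 for mTSS so that the two sections agree, specify a separate unstructured covariance matrix for each treatment group (REPEATED with GROUP=treatment). Keep Kenward-Roger and the rest of the model. At a minimum, add this as a pre-specified sensitivity analysis. If sandwich standard errors are preferred, respecify the degrees-of-freedom method, because Kenward-Roger adjusts the model-based covariance that the sandwich replaces.

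Write it in before the Week 24 unblinding, which is when SAP Section 1 says the plan will be final; a choice made after seeing the SDs by arm would look data-driven.

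The cost is a sentence in each section and one SAS option. With two postbaseline visits a matrix has 3 parameters, so four arms need 12, nine more than now, with about 1650 subjects to estimate them. The interval against placebo becomes slightly wider if the spreads differ, and hardly changes if they do not.
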